11.2. Sample Size Determination

The primary clinical outcome is OMAS at 4 months. Previous studies have demonstrated a minimally clinical important difference (MCID) of 10 points, ^{3 32} which is in accordance with expert opinion (for scales scoring 0-100) and statistical convention. ^{3 33} We have selected a standard deviation (SD) of 21.8 based on the largest published RCT studying the OMAS within six months of surgically treated ankle fracture. ³ Although AIM included participants aged over 60 years we are not expecting the variability in OMAS in participants aged 60 years and younger to be different. A non-inferiority margin of 5 points has been chosen. This is half the MCID (one method of choosing the non-inferiority margin) and this has been discussed with clinical experts who felt that this would provide enough evidence to change clinical practice, whereas using 6 points (as AIM used for its equivalence margin) would be less convincing in this patient population.

800 participants providing data at four months will provide 90% power and 2.5% (1-sided) significance to detect whether non-surgical treatment for the treatment of unstable ankle fractures is non-inferior to surgical treatment using a non-inferiority margin of -5 points on the OMAS score at four months. Allowing for 10% loss to follow-up, this yields an overall target of 890 participants (445 per arm). ³⁴ Essentially the lower 95% confidence interval of the treatment difference is assessed against the non-inferiority margin

of -5 points and if it lies above this then the trial will be assessed as non-inferior. If non-surgical management is found to be non-inferior to surgical management of unstable ankle fractures then superiority will also be tested at 2.5% (1-sided) significance (the equivalent of comparing the lower 95% confidence interval against Zero rather than -5 points).

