Where severe departure from normality is identified, the first approach will be data transformation. If the data cannot be transformed to normality then the Mann-Whitney U test will be used (in this case, no further adjustments will be made). The primary focus will be the comparison of the two treatment groups of participants, and this will be reflected in the analysis which will be reported together with appropriate diagnostic plots that check the underlying model assumptions. The adjusted analysis using the perprotocol population will be considered the primary analysis to determine non-inferiority and superiority (if shown to be non-inferior) with the additional analyses, including using the intention-to-treat population, providing supporting evidence. Secondary clinical outcomes will be similarly analysed using mixed effects regression, using logistic regression for binary data and linear regression for continuous data.

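### The fallback for non-normal OMAS (transformation, then an unadjusted Mann-Whitney U test) does not, as written, produce the interval in OMAS points that the −5 rule needs

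*Protocol*

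**What the plan says.** Section 11.2 sets the margin on the raw scale ("A non-inferiority margin of 5 points has been chosen") and the decision rule: "the lower 95% confidence interval of the treatment difference is assessed against the non-inferiority margin", which is −5 points. If non-inferiority is shown, the same limit is compared with zero for superiority.

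Section 11.4 repeats the rule. It lists four possible results for the primary endpoint, each defined by where the confidence interval lies relative to the margin or to zero. The treatment difference comes from adjusted means in a mixed-effects linear model, with centre as a random effect and adjustment for baseline OMAS, age, gender and fracture stability.

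The same section then gives a fallback in two steps. Step one: "Where severe departure from normality is identified, the first approach will be data transformation". Step two applies when no suitable transformation is found: "If the data cannot be transformed to normality then the Mann-Whitney U test will be used". That test carries no covariates. Shortly afterwards the section says that the adjusted per-protocol analysis is the one that determines non-inferiority and superiority.

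**The concern.** The rule needs a 95% confidence interval for a difference in OMAS points. The fallback replaces the analysis that supplies this interval with two methods that, as described, do not. The protocol gives no transformed margin, no back-transformation, no rank-based interval and no margin-shifted rank test.

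The fallback also conflicts with the text around it. An unadjusted rank test cannot be the adjusted analysis that Section 11.4 says determines non-inferiority, and Section 11.4 also says that all analyses adjust for important baseline covariates.

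At stake is the trial's headline conclusion. If the trigger were met, the team would have to choose a margin or method after seeing the distribution of the outcome, or set the fallback aside. The trigger is a judgement on the trial's own data, so the method behind the primary conclusion would depend on those data.

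**Working it through.** **Inputs.** From Section 11.2: margin 5 points; "We have selected a standard deviation (SD) of 21.8"; "800 participants providing data at four months will provide 90% power and 2.5% (1-sided) significance"; 10% loss. From Section 7: 1:1 allocation. Assumed: a true difference of 0, which is not stated but reproduces the size.

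**1. The planned size rests on a raw-scale mean difference.**
- n per arm = 2(1.960 + 1.282)² × 21.8² / 5² ≈ 399.5, so 400 per arm and 800 in total. Power at 400 per arm is 90.0%.
- 800 / 0.9 = 888.9, so 889, or 890 in equal arms. The stated figures reproduce.
- Standard error = 21.8 × √(2/400) = 1.54; half-width of the 95% interval = 1.96 × 1.54 = 3.02 points.

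**2. Transformation.** Take a control score x and a score 5 points lower.

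| Scale | Formula for 5 points | x = 60 | x = 90 | Ratio |
|---|---|---|---|---|
| Reflected log | ln[(101 − (x − 5)) / (101 − x)] | ln(46/41) = 0.115 | ln(16/11) = 0.375 | 3.3 |
| Square | x² − (x − 5)² | 3600 − 3025 = 575 | 8100 − 7225 = 875 | 1.5 |

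The reflected log and the square are illustrations; the protocol names no transformation. The −5 margin becomes a different number at each control score, so a confidence interval on the transformed scale has no fixed value to be compared with.

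**3. Mann-Whitney U test, set beside the rule.**
- The rule needs a null of −5 points; the test as named has a null of no difference.
- The rule needs an interval in OMAS points; the test as named gives a p-value. None of the four results listed in Section 11.4 can be assigned from it.
- Section 11.4 makes the adjusted analysis decisive; the test drops centre, fracture stability, age, gender and baseline OMAS.

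**4. Is the fallback needed?** Section 11 itself plans a normal approximation for OMAS. The documents give no OMAS distribution, so these are assumed ones: bounded 0–100 scores in steps of 5, 400 per arm, with the ordinary unadjusted 95% interval for the mean difference.
- Clipped normal (control mean 69.3, SD 25.4, skew −0.57, about 20% at the ceiling), 4,000 trials at a true −5: non-inferiority falsely declared in 2.3%.
- Beta(1.9, 0.75) × 100 (skew −0.78, about 10% at the ceiling), 20,000 trials: 2.4%, with 95.0% coverage.
- Across all runs the range was about 2.3–2.8%, against a nominal 2.5%.

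The raw-scale interval therefore remains usable under strong skew and a ceiling at this sample size.

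**The case against.** **The surrounding text points to the confidence interval.** Section 11.4 promises 95% intervals and a figure showing them against the margin, and it makes the adjusted analysis decisive. One could read the rank test as an extra comparison that leaves the rule untouched. But the fallback is worded as what will be used instead, with no adjustment, and nothing says that the adjusted raw-scale interval is kept for the decision. At best the passages conflict and must be reconciled.

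**Details belong in the analysis plan.** Section 11.1 defers full details to a plan not shown here. A criterion for severe non-normality, or a back-transformation, could properly sit there. The protocol, however, itself fixes a named fallback, and that is what fails to match its own rule.

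**Suitable methods exist.** This stands. A Hodges-Lehmann interval, a margin-shifted rank test or a back-transformed mean difference could be set against −5 points. A reader might infer that the primary question could never be answered after a transformation or a rank analysis; that goes too far. But the protocol names none of these, and some need a pure-shift assumption. In the clipped-normal simulation above, a rank test shifted by 5 points had 4.2% one-sided error against 2.5%, because that assumption fails at the ceiling.

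**Would a non-significant Mann-Whitney result be read as non-inferiority?** A reader might fear so, but the protocol never says it; Section 11.4 allows that conclusion only from a confidence interval. Nor is there one error rate to quote. At a true −5 the test was non-significant in roughly 6% to 30% of simulated trials, depending on how the deficit was generated. Part of this is ordinary type II error: at SD 21.8 and 400 per arm, a t-test of no difference has 90% power for 5 points, so it misses about 10%.

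**The harm is conditional.** This also stands. It needs a severe departure and, for the rank test, a failed transformation. Skew is plausible on a bounded score, but the documents do not show that the trigger is likely to be met.

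**Conclusion.** The fallback is wrong as written. If triggered, the non-inferiority rule of Sections 11.2 and 11.4, and the superiority comparison tied to it, could not be applied without a margin or method that the protocol does not give. If it is not triggered, the planned primary analysis stands.

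The conflict follows from the text and needs no assumption about the data. The finding that the fallback is unnecessary rests on assumed score distributions, 400 per arm and an unadjusted interval; the mixed model itself was not simulated. The documents do not support saying that the trial cannot answer its question, or attaching a particular false-conclusion rate to the fallback. The sample size of 800 evaluable and 890 recruited is correct on its stated inputs and is unaffected.

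**What to change.** Replace the two fallback sentences in Section 11.4, for OMAS at four months, with a statement to this effect:

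- The comparison with −5, and the superiority test that follows it, always use the adjusted mean difference on the raw 0–100 scale from the planned mixed model.
- If residuals are badly non-normal or heteroscedastic, the 95% confidence interval for that same difference comes from robust (sandwich) standard errors or a bootstrap.
- Transformed or rank-based analyses are supportive only and do not decide non-inferiority or superiority.

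Carry the same wording into the analysis plan before the primary outcome analysis. The cost is a sentence or two and, if triggered, one bootstrap run; Section 11.5 already plans bootstrap intervals for the economic results. No extra participants or data are needed.

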10.3. Reporting Procedures for Adverse Events not defined as serious

Adverse events that are unrelated to the intervention or treatment will not be reported.

Adverse events (AEs) that are foreseeable in the treatment of these fractures, and are not defined as SAEs, do not need to be reported immediately, provided they are recorded in the 'Complications' section of the Case Report Forms and/or Patient Questionnaires.

Other adverse events, foreseeable or unforeseeable, that are not in this list, will not be reported.

Foreseeable, related AEs include the following:

- (a) Related to CCC only:
- o loose cast or tight cast requiring reapplication
- failed closed reduction
- o pressure ulcer
- o plaster saw laceration
- (b) Related to surgical treatment only:
- o surgical site infection
- failed fixation
- o prominent implant
- wound dehiscence
- vascular injury

- (c) Related to both treatments:
- o revision surgery, defined as unplanned return to theatre
- symptomatic deep venous thrombosis
- o symptomatic pulmonary embolus
- o compartment syndrome
- o nerve palsy
- o complex regional pain syndrome
- pain/irritation/itchiness from cast

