11.4. Description of the Statistical Methods

In non-inferiority trials we want to show that the new treatment is not clinically worse than the active control and therefore the interest is one-sided. The new treatment may be better than the control, but it is at least non-inferior to it. We define a non-inferiority margin (Δ_T), which is the maximum difference we are prepared to tolerate in a given direction that the new treatment is not to be considered clinically inferior to the well-established standard treatment. The null hypothesis is therefore that a difference of greater than Δ_T exists in favour of the standard treatment (H₀: $\Delta \le -\Delta_T$) (Δ defined as the difference between treatment and control (T-C)) and the trial is targeted at disproving this in favour of the alternative that the new treatment is non-inferior (H_A : $\Delta \ge -\Delta_T$). This will be assessed by creating a 95% confidence interval which should be entirely above the non-inferiority margin for the new treatment to be declared noninferior. FDA regulations recommend that both a treatment received (per protocol) and intention to treat (ITT) analysis is performed aiming to demonstrate non-inferiority. Use of the ITT approach as in a superiority trial sometimes increases the chance of falsely claiming non-inferiority. Therefore, the primary analysis will be undertaken on the per-protocol population, where only those patients who received their allocated treatment will be analysed and those that do not will be excluded from the analysis. A secondary analysis will be undertaken on the ITT population where all randomised patients will be analysed according to their treatment allocation.

The result of the analysis for the primary endpoint should be one of the following:

- The confidence interval for the difference between the two treatments lies entirely above the noninferiority margin (-ΔT), so that non-inferiority may be concluded with only a small probability of error.
- The confidence interval includes points below the non-inferiority margin, then there is a possibility that the new treatment is inferior to the control and non-inferiority cannot be safely concluded.
- The confidence interval is entirely above zero, indicative of a treatment effect, then superiority of the new treatment can be concluded within a small probability of error.

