11.8. The Level of Statistical Significance

One-sided 2.5% significance will be used for the non-inferiority comparisons. For superiority comparison and secondary outcome analyses 5% (2-sided) significance will be used.

11.9. Procedure for Accounting for Missing, Unused, and Spurious Data.

Missing data, e.g. due to withdrawal, protocol violation or patient loss to follow-up will be summarised and patterns analysed. The primary analysis method is reasonably robust to missing at random data where

all available data at all time-points is utilised.⁴¹ Sensitivity analyses will assess departures from the missing at random assumptions using multiple imputation techniques if appropriate.

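### The superiority test on OMAS is governed by the per-protocol analysis, although the only reason given for per-protocol applies to non-inferiority

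*Protocol*

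**What the plan says.** **Superiority.** The design section (7) and section 11.2 plan a formal superiority test once non-inferiority is shown. Section 11.2 states that "superiority will also be tested at 2.5% (1-sided) significance". Section 11.8 puts it as "For superiority comparison and secondary outcome analyses 5% (2-sided) significance will be used". Both give the same critical value, 1.96.

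**Analysis set.** Section 11.4 says that the adjusted analysis in the per-protocol "population will be considered the primary analysis to determine non-inferiority and superiority (if shown to be non-inferior"). The other analyses, ITT among them, are there to support it. The reason given for per-protocol is that "Use of the ITT approach as in a superiority trial sometimes increases the chance of falsely claiming non-inferiority". No reason is given for using it to judge superiority.

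**Who is in the set.** Sections 11.3 and 11.4 keep only patients who received the treatment they were allocated; section 11.3 also removes major deviations. Section 9.6.2 provides for conversion from casting to open fixation during the procedure if an acceptable closed reduction is not achieved, and says that this is not a protocol violation. It does not say whether these patients stay in the per-protocol set.

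**Secondary outcomes.** Section 11.4 says "Secondary clinical outcomes will be similarly analysed using mixed effects regression" and names no population. Section 10.3 lists "failed closed reduction" among the foreseeable casting-only events.

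**The concern.** In a non-inferiority test, departures from allocated treatment tend to pull the arms together under ITT, which can help a false claim. That is a fair reason for wanting a per-protocol analysis there. For superiority the same dilution works against a claim, so ITT is usually the cautious set. Section 11.4 itself associates ITT with superiority trials, then gives the superiority decision to per-protocol.

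The exclusions may also be lopsided. The protocol describes a route from casting to fixation after failed reduction, and no matching route in the surgical arm. If converted patients leave the per-protocol set and would have scored worse than those who stay, the cast-arm mean rises for a reason unrelated to treatment benefit. Section 9.4 says the trial compares treatment pathways. A per-protocol superiority claim could then describe only patients in whom casting succeeded.

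Testing non-inferiority first gives no protection, because any interval wholly above zero is already above -5. If the two sets disagree on superiority, section 11.4 lets per-protocol decide.

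**Working it through.** **1. The plan's own figure.** Inputs from section 11.2: SD 21.8, margin 5, true difference 0, one-sided 2.5%, power 90%.

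- n per arm = 2 × 21.8² × (1.960 + 1.282)² / 5², which gives 400 after rounding up, so 800 in total.
- 800 / 0.90 = 888.9, so 889, or 890 with equal arms.

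This reproduces the statement that "800 participants providing data at four months will provide 90% power and 2.5% (1-sided) significance" and the target of 890. No stated figure is wrong.

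**2. False superiority under selective exclusion.** The documents do not give the two key inputs, so they are assumptions:

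- f = share of the casting arm excluded from per-protocol
- g = how many OMAS points lower the excluded cast patients score than those retained

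Further assumptions are a true difference of 0 over all randomised participants, 400 evaluable per arm before exclusions, and no exclusions from the surgical arm.

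If the whole casting arm has the same mean as surgery, the retained cast patients sit f × g above it. Then:

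- bias = f × g
- SE = 21.8 × √(1/(400(1 − f)) + 1/400)
- one-sided error = 1 − Φ(1.96 − bias/SE)

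With g = 10:

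| f | bias | SE | 1.96 − bias/SE | error |
|---|---|---|---|---|
| 0% | 0 | 1.541 | 1.960 | 2.5% |
| 2% | 0.2 | 1.549 | 1.831 | 3.4% |
| 5% | 0.5 | 1.562 | 1.640 | 5.1% |
| 10% | 1.0 | 1.584 | 1.329 | 9.2% |
| 15% | 1.5 | 1.608 | 1.027 | 15.2% |

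Range over g: at f = 2% and g = 5 the error is 2.9%; at f = 10% it is 5.0% for g = 5 and 24.3% for g = 20. A simulation with 10,000 trials per scenario gave 4.7% at f = 5% and 8.8% at f = 10% (both g = 10). The ITT error stayed between 2.3% and 2.5%.

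**3. When the bias vanishes.** If g = 0, the bias is 0. If g is negative, it works against casting. If a share f₀ of the surgical arm is also excluded and scores g₀ lower than the rest, the net bias is f × g − f₀ × g₀, which is zero when the two products match.

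**4. Complications, conditional on two readings.** Suppose per-protocol were used and conversions were excluded. Take an illustrative true rate of 15% in both arms (not from the documents), with every excluded patient counting as an event. The per-protocol casting rate is (0.15 − f)/(1 − f):

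- f = 2%: 0.13/0.98 = 13.3%
- f = 5%: 0.10/0.95 = 10.5%
- f = 10%: 0.05/0.90 = 5.6%

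These would be apparent advantages for casting of 1.7, 4.5 and 9.4 percentage points where none exists.

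**The case against.** Three stronger readings are tempting, and the documents support none of them as fact.

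- **Secondary outcomes and complications are led by per-protocol.** A reader might infer this because the sentence on secondary outcomes follows directly after the one giving per-protocol the lead. But that sentence is about model type and names no population. The opening of section 11 assesses OMAS differences on both sets, including at the additional time-points, and section 11.5 runs the economic analyses on both. The lead set is simply not stated, and a protocol may leave it to the analysis plan.
- **Failed closed reductions are zero in the per-protocol set by construction.** This follows only from a literal reading of sections 11.3 and 11.4. Section 9.6.2 points the other way, and it makes conversion depend on clinical appropriateness, so not every failed reduction converts. Sections 11.1 and 11.3 leave the final set to a blinded review. Casts that fail later did receive the allocated treatment and are not clearly excluded.
- **Per-protocol exclusions are always anti-conservative.** They can be. Converted patients receive standard-of-care fixation and may do no worse than those retained. Exclusions will also occur in the surgical arm.

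It is also fair to say that superiority is a conditional second step, that ITT results will be reported, and that section 11.4 plans sensitivity analyses for protocol deviations. A superiority result confined to per-protocol would be visible.

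All this limits the severity. It does not answer the main point: the plan expressly gives the superiority decision to per-protocol and gives no reason that applies to it.

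**Conclusion.** The point holds for the superiority test on OMAS, where the assignment to per-protocol is explicit. Its effect on the error rate is conditional. If few patients are excluded the inflation is small (3.4% at 2% excluded, with a 10-point deficit); at 10% to 15% excluded it is material (9.2% to 15.2%). All these values rest on an assumed exclusion share, an assumed deficit and no exclusions in the surgical arm.

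The per-protocol status of intra-operative conversions is a separate ambiguity between section 9.6.2 and sections 11.3 and 11.4, and these must be reconciled. For secondary outcomes and complications the finding is only that no lead set is named and that one possible choice would under-count failed closed reductions in the casting arm.

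Severity: should-fix. The sample size is not in question, and this point does not challenge the use of per-protocol in the non-inferiority decision.

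**What to change.** In section 11.4:

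1. Limit per-protocol primacy to the non-inferiority decision, read alongside ITT.
2. Make ITT primary for superiority on OMAS, with per-protocol as a sensitivity analysis. Define ITT here as all randomised participants as allocated, because section 11.3 currently restricts it to those with data at every time-point to 12 months.
3. State that secondary outcomes and complication comparisons also lead with all randomised participants.

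Reconcile section 9.6.2 with sections 11.3 and 11.4, so that it is clear before any outcome is seen whether intra-operative conversions belong to the per-protocol set.

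The cost is protocol and analysis-plan wording. No new data are needed, and the target of 890 is unchanged.
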